#### **8.6.1.5 Adverse events by dose immediately before onset**

The number and incidence rate of adverse events and adverse drug reactions in overall and individual events classified by SOC and PT per total exposure period should be calculated for each treatment group by dose immediately before onset\*. The total exposure period is defined as the total number of months (months) that each dose was administered during the study period.

The following formula is used to calculate the number of months of exposure.

$$\text{Number of months of exposure} = \text{number of days of exposure}/30.4375$$

\* The tabulation unit for each event by dose immediately before onset should be as follows:

MT-6548 group: daily dose (tabulation unit: 0 mg, 150 mg, 300 mg, 450 mg, 600 mg)

Darbepoetin group: weekly dosage (tabulation unit: 0 µg, >0 µg to ≤30 µg, >30 µg to ≤60 µg, >60 µg to ≤90 µg, >90 µg to ≤120 µg, >120 µg)

#### **8.6.1.6 Adverse events by cumulative dosage**

The number of subjects and incidence rate should be calculated for adverse events and adverse drug reactions by cumulative dosage before onset for the overall and for individual events classified by SOC and PT. The cumulative dosage will be divided into 4 categories at quartiles (0 to 1/4 of the maximum cumulative dosage, 1/4 to 2/4 of the maximum cumulative dosage, 2/4 to 3/4 of the maximum cumulative dosage, and ≥3/4 of the maximum cumulative dosage). In addition, the average number of exposure days per person should be calculated for each category. (Average number of exposure days: in the case of “0–x/4 \* Maximum Cumulative dosage”, the number of days until the subject concerned reaches x/4 \* maximum cumulative dosage should be calculated for each subject. In the case of ≥3/4 \* maximum cumulative dosage, the number of days to final administration for each subject and the mean should be calculated.)

\* The tabulation unit by cumulative dosage is as follows: However, if the same adverse event occurs in different categories in the same subject, it is counted as 1 subject in each category.

4 categories (tabulation unit: 0 to <1/4 of the maximum cumulative dosage, 1/4 to < 2/4 of the maximum cumulative dosage, 2/4 to <3/4 of the maximum cumulative dosage, ≥3/4 of the maximum cumulative dosage).

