#### **8.6.1.6 Adverse events by cumulative dosage**

The number of subjects and incidence rate should be calculated for adverse events and adverse drug reactions by cumulative dosage before onset of AE for the overall events and for individual events classified by SOC and PT. The cumulative dosage will be divided into 4 categories at quartiles (0 to 1/4 of the maximum cumulative dosage, 1/4 to 2/4 of the maximum cumulative dosage, 2/4 to 3/4 of the maximum cumulative dosage, and ≥3/4 of the maximum cumulative dosage). In addition, the average number of exposure days per person should be calculated for each category. (Average number of exposure days: in the case of “0 to x/4 of the maximum cumulative dosage”, the number of days until the subject concerned reaches x/4 of the maximum cumulative dosage should be calculated for each subject. In the case of ≥3/4 of the maximum cumulative dosage, the number of days to final administration for each subject and the mean should be calculated.)

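### The adverse-event table by cumulative dose counts events within separate dose bands but exposure days from the start of treatment, so the two do not match in bands 2 to 4

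*SAP*

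**What the plan says.** Final SAP 8.6.1.6 sets three rules for this table.

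- Events: "The number of subjects and incidence rate should be calculated for adverse events and adverse drug reactions by cumulative dosage before onset". The tabulation units do not overlap; the middle two are "1/4 to < 2/4 of the maximum cumulative dosage, 2/4 to <3/4 of the maximum cumulative dosage". A repeat event is handled band by band: "if the same adverse event occurs in different categories in the same subject, it is counted as 1 subject in each category".
- Exposure: "the average number of exposure days per person should be calculated for each category".
- Definition of those days: for an interval labelled as running from zero to x/4 of the maximum, "the number of days until the subject concerned reaches x/4" of that maximum. For the top band it is "the number of days to final administration for each subject and the mean should be calculated".

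Phase 1 SAP 8.6.1.6 uses the same exposure rule: "the number of days until the subject concerned reaches x/4 of the maximum cumulative dosage should be calculated for each subject".

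The section names no denominator for the incidence rate. It does not say whether the maximum is the subject's own total or the largest total in the arm, and it gives no value for a subject who never reaches x/4.

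**The concern.** The event column and the exposure column are presented for the same four categories but describe different stretches of time. An event in the third band occurred after half of the maximum had been accumulated. The exposure printed for that band runs from the first dose, so it also includes the time spent in bands 1 and 2. Only the first band is consistent.

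Exposure days are printed beside event counts so that frequency can be judged against time at risk. A reader who does that here divides by too many days in bands 2, 3 and 4. The error grows with the band number in all the dose paths worked below, so it runs in the reassuring direction: a flat event frequency would look as if it fell with accumulating dose. Safety of long-term administration is one of the trial's stated objectives (Protocol section 2), so the table should not mislead on that point.

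**Working it through.** The documents give no exposure-day figure for this table, so there is none to reproduce. The check applies the rule to dose paths within the protocol's range.

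**Inputs.** Daily dose 150 to 600 mg (Protocol 8.3.3). Start at 300 mg (8.3.2). Increases of one tablet at a time, at intervals of at least 4 weeks in principle (8.3.3). Dosing to the day before Week 52 (8.4), taken as 364 days. The SAP does not write out where the count starts; I assume the first dose, which the zero-to-x/4 label implies.

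**Formulas.** Let M be the maximum and T(x) the day on which cumulative dose reaches x/4 of M.

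- Plan's days for band x = T(x); for band 4, the day of the last dose.
- Days actually in band x = T(x) − T(x−1), with T(0) = 0; for band 4, last dose − T(3).
- Factor = plan's days ÷ days in band.

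**M = the subject's own total.**

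| Dose path | Total (mg) | Plan's days, bands 1–4 | Days in band | Factor, bands 2/3/4 |
|---|---|---|---|---|
| Constant dose, 364 d | 364 × dose | 91/182/273/364 | 91/91/91/91 | 2/3/4 |
| 300 mg 84 d, 150 mg 280 d | 67,200 | 56/140/252/364 | 56/84/112/112 | 1.67/2.25/3.25 |
| 300 mg 28 d, 450 mg 28 d, 600 mg 308 d | 205,800 | 106.75/192.5/278.25/364 | 106.75/85.75/85.75/85.75 | 2.24/3.24/4.24 |
| 300 mg 182 d, 600 mg 182 d | 163,800 | 136.5/227.5/295.75/364 | 136.5/91/68.25/68.25 | 2.50/4.33/5.33 |
| 300 mg 168 d, 450 mg 112 d, 600 mg 84 d | 151,200 | 126/224/301/364 | 126/98/77/63 | 2.29/3.91/5.78 |

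Worked for the second row: a quarter of 67,200 is 16,800 mg, reached on day 16,800/300 = 56. Half is 33,600 mg; 25,200 mg is in by day 84 and the other 8,400 mg takes 8,400/150 = 56 days, so day 140. Band 2 lasts 140 − 56 = 84 days, and 140/84 = 1.67.

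**M = an assumed trial-wide maximum.** Take the fastest up-titration at 4-week intervals: 300 × 28 + 450 × 28 + 600 × 308 = 205,800 mg.

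- Constant 450 mg: three quarters (154,350 mg) is reached on day 343, so 21 days fall in band 4. The factor is 364/21 = 17.3.
- 300 mg for 182 days, then 600 mg: band 4 is entered on day 348.25, leaving 15.75 days. The factor is 364/15.75 = 23.1.
- Constant 300 mg: half (102,900 mg) is reached on day 343, so 21 days fall in band 3. Three quarters is never reached, and the rule gives no value for band 3.

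**Effect on a reader.** With a constant frequency of e events per day at a constant dose, each band holds about 91e events. Divided by the plan's days this reads e, e/2, e/3 and e/4. Conversely, true frequencies of e, 2e, 3e and 4e would read as flat.

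**The case against.** Three points can be made for the plan.

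*The incidence rate is not built on these days.* This stands. The exposure days are an added item, and nothing in 8.6.1.6 divides by them. Where the SAP wants an exposure-based rate it says so, as in 8.6.1.5, which works per total exposure period. A reader might infer that the planned incidence is itself miscalculated; the text does not support that.

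*The interval is labelled as starting from zero.* This is true, and if the column were headed as cumulative time to a threshold, much of the problem would go. But the SAP asks for the figure for each category, and the table has no categories running from zero to 2/4 or from zero to 3/4.

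*The table is supplementary.* This also stands. It is descriptive, with no test or decision attached. Long-term safety is also covered by events by time of onset to Day 365 and beyond (8.6.1.4), events by dose per exposure period (8.6.1.5), liver function criteria (8.6.3) and high Hb values (8.6.9).

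The missing incidence denominator and the undefined maximum are ambiguities to settle, not demonstrated errors. By contrast, 8.6.1.4 and 8.6.1.7 do name their denominators.

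**Conclusion.** The point holds for the exposure column. Followed as written, the rule gives a wrong per-band exposure for bands 2 to 4 for any subject who spent time in a lower band. The first band is unaffected.

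The size depends on assumptions. A reader might take a 2 to 4 fold overstatement as general. The factors 2, 3 and 4 need a constant dose and a full quarter of the maximum accumulated in every band. Over the paths tried, with own total as the maximum, the range was 1.67 to 5.78. With a trial-wide maximum the top-band factor can be far larger for subjects who only just pass three quarters.

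A reader might also take 600 × 364 = 218,400 mg as the arm maximum and conclude that a subject on 300 mg throughout (109,200 mg) never spends time in the upper two bands. The protocol's 300 mg start and stepwise increases do not fit that maximum. Against 205,800 mg, such a subject spends 21 days in band 3.

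The planned incidence is not shown to be wrong. The consequence is a table that understates event frequency at higher cumulative dose if its columns are compared. Severity: minor.

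**What to change.** In final SAP 8.6.1.6:

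1. Define exposure for band x as days from reaching (x−1)/4 of the maximum to reaching x/4 or to the last dose, whichever comes first; for the top band, from reaching 3/4 to the last dose. Average it over subjects who entered the band.
2. Use the subjects who entered the band as the incidence denominator.
3. State whether the maximum is per subject or per arm.

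Step 1 also settles what happens to a subject who enters a band without completing it. If the present definition is kept, the column should at least be headed as cumulative days from the first dose.

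Final SAP 8.5.4.3 says the phase 1 analysis has already been conducted, so that table should be relabelled or re-tabulated.

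The cost is SAP wording and a small additional derivation from dosing records already held. No new data are needed.

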#### 8.6.1.7 Adverse events before and after drug interruption

For adverse events and adverse drug reactions, the number of subjects in the overall and in individual events classified by SOC and PT and the incidence rate to subjects with drug interruption should be calculated in before and after interruption of the active drug. It is classified to 2 categories: 4 weeks before drug interruption and 4 weeks after drug interruption (4 weeks after the start of drug interruption). If a subject has had multiple interruptions, a second interruption within 4 weeks of the first interruption is counted both 4 weeks before and 4 weeks after the first interruption.

Drug interruption period is defined as the period when “Yes” was selected in the question of “Did you choose the dosage according to the dosage adjustment algorithm?” and “0 mg” for the MT-6548 group or “0 µg” for the darbepoetin group was selected in the question of “Whether the dose was changed” in the “Administration status” of the case report form. If “No” is selected in the question of “Did you choose dosage according to dosage adjustment algorithm?”, the subject should not be included in the calculation.

#### 8.6.2 Laboratory test values

Descriptive statistics (except 2-sided 95% CI of the mean) should be calculated by treatment group at each evaluation time point for hematology tests, blood biochemistry tests, C-reactive protein, VEGF, and dehydroepiandrosterone sulfate (hereinafter, DHEA-S). Changes from the first day of the treatment period at each evaluation time point should also be summarized.

#### 8.6.3 Number and proportion of subjects whose liver function values meet interruption/discontinuation criteria of the study drug

For AST and ALT, the number and proportion of subjects who meet the following conditions should be provided in each period between scheduled hospital visits from the first day to Week 52 week of the treatment period and during the entire treatment period from the first day to Week 52 of the treatment period. However, the conditions of each laboratory test values should be as shown in Table 8.6.3.1.

Table 8.6.3.1 Definition of tabulation conditions for liver function values

Tabulation condition	Definitions
AST, ALT	AST >3.0 × ULN and total bilirubin $\leq$ 2.0 × ULN ALT >3.0 × ULN and total bilirubin $\leq$ 2.0 × ULN AST >3.0 × ULN and total bilirubin >2.0 × ULN ALT >3.0 × ULN and total bilirubin >2.0 × ULN AST >5.0 × ULN ALT >5.0 × ULN AST >8.0 × ULN

	ALT > 8.0 × ULN
--	-----------------

#### **8.6.4 Resting standard 12-lead ECG**

The frequency of each decision result (normal, clinically nonsignificant abnormal, or clinically significant abnormal) should be calculated at each evaluation time point, and a shift table composed of the decision results on the first day of the treatment period and each evaluation period should be provided.

#### **8.6.5 Kt/V, Body weight after dialysis and dry weight**

Descriptive statistics (except for 2-sided 95% CIs of mean) should be calculated for each treatment group by evaluation time point. Changes from the first day of the treatment period at each evaluation time point should also be summarized.

#### **8.6.6 Vital signs**

Descriptive statistics (except for 2-sided 95% CIs of mean) should be calculated for each treatment group by evaluation time point for the items of blood pressure and pulse rate. Changes from the first day of the treatment period at each evaluation time point should also be summarized.

#### **8.6.7 Fundoscopy**

The frequency of each decision result (normal, clinically nonsignificant abnormal, or clinically significant abnormal [Presence or absence of retinal hemorrhage, presence or absence of retinal edema]) should be calculated at each evaluation time point, and a shift table composed of the decision results (normal, clinically nonsignificant abnormal, or clinically significant abnormal) should be provided on the first day of the treatment period and each evaluation time point.

#### **8.6.8 Chest X-ray**

The frequency of each decision result (normal, clinically nonsignificant abnormal, or clinically significant abnormal) should be calculated at each evaluation time point, and a shift table composed of the decision results on the first day of the treatment period and each evaluation period should be provided.

#### **8.6.9 Proportion of subjects with documented Hb values of $\geq 12.0$ g/dL or $\geq 13.0$ g/dL**

The number, proportion, and 95% CI (Clopper-Pearson [Exact] method) of subjects with confirmed Hb  $\geq 12.0$  g/dL or  $\geq 13.0$  g/dL, after the first day of the treatment period, in each period between scheduled study visits and during the entire treatment period from the first day to Week 52 of the

treatment period should be provided for each treatment group. If Hb is  $>12.0$  g/dL or  $13.0$  g/dL in the same subject, the subject should be counted in both categories.

#### **8.6.10 Proportion of subjects with documented Hb values of $<9.0$ g/dL or $<8.0$ g/dL.**

Subjects with confirmed Hb values  $<9.0$  g/dL or  $<8.0$  g/dL should be analyzed in the same manner as in Section 8.6.8.

#### **8.6.11 Proportion of subjects with a documented Hb increase rate $>0.5$ g/dL/week**

The number, proportion, and 2-sided 95% CI (Clopper-Pearson [Exact] method) of subjects with confirmed Hb increase rate of  $\geq 0.5$  g/dL/week, after the first day of the treatment period, in each period between scheduled study visits and during the entire treatment period from the first day to Week 48 of the treatment period should be provided for each treatment group. The Hb increase rate in this tabulation should be calculated based on the difference in Hb values in each period between scheduled study visits in every 4 weeks and the treatment interval obtained from the actual study visit date.

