7.2 Safety endpoints

- (1) Adverse events and adverse drug reactions
- (2) Laboratory test values
- (3) Resting standard 12-lead ECG
- (4) Dry weight
- (5) Body weight
- (6) Vital signs
- (7) Fundoscopy
- (8) Chest X-ray
- (9) Proportion of subjects with documented Hb levels of ≥ 12.0 or ≥ 13.0 g/dL
- (10) Ratio of subjects with Hb increase rates exceeding 0.5 g/dL/week.

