13.3.3 Safety

(1) Analysis methods for AEs and ADRs

The following statistics will be shown by treatment group: numbers of subjects and incidence ratios for AEs, SAEs, AEs leading to discontinuation, AEs leading to death, ADRs, serious ADRs, ADRs leading to discontinuation, and ADRs leading to death.

(2) Analysis methods for laboratory values, resting standard 12-lead ECG, dry weight, body weight, vital signs, fundoscopy, and chest X-ray

Descriptive statistics will be calculated for continuous data at each timepoint by treatment group. Descriptive statistics will also be calculated for changes from baseline by treatment group. A shift table will be shown for changes of discrete data from baseline to each timepoint by treatment group.

(3) Analysis methods for ratios of subjects with Hb levels of ≥ 12.0 g/dL or ≥ 13.0 g/dL.

Numbers and ratios of subjects with Hb levels of ≥ 12.0 g/dL or ≥ 13.0 g/dL at each timepoint will be shown by treatment group.

(4) Ratio of subjects with Hb increase rates exceeding 0.5 g/dL/week.

Numbers and ratios of subjects with rate of Hb increase of >0.5 g/dL/week will be shown by treatment group.

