## Definitions of Terms

Term	Definitions
Study period	From the day of informed consent to the final day of the follow-up observation period
Treatment period	From the first day of the treatment period to the final day of the treatment period
Treatment period phase 1	From completion of scheduled tests for the first day of the treatment period to completion of scheduled tests for Week 24 of the treatment period
Treatment period phase 2	From completion of scheduled tests for Week 24 of the treatment period to completion of scheduled tests for Week 52 of the treatment period
Day of completion of treatment period	Week 52 of the treatment period or the day of discontinuation during the treatment period
X weeks prior to the first day of the screening period	Same day of the week X weeks prior to the first day of the screening period
MT-6548 tablets	Film-coated tablets containing 150 mg of vadadustat per tablet
Darbepoetin alfa injection	Plastic syringe containing darbepoetin alfa (recombinant) in 1 syringe (0.5 mL)
Conversion cohort	Patients who have received the same ESA formulations from 8 weeks prior to the first day of the screening period

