### **8.5.2 Analysis of other endpoints**

- (1) Number of days to maintain the target Hb values

The total number of maintenance days from the state meeting the target Hb range to leaving the target Hb range should be calculated for each subject, and the descriptive statistics should be calculated. Only the MT-6548 group is analyzed. However, if treatment period is completed in 52 weeks, the maintenance days should be until Week 52 of the treatment period.

- (2) Proportion of subjects who received rescue therapy with ESA, blood transfusion, or phlebotomy

The number, proportion, and 95% CI (Clopper-Pearson [Exact] method) of the proportion of subjects receiving rescue therapy with an ESA preparation should be provided by treatment group, after the first day of the treatment period, in each period between scheduled study visits and during the entire treatment period from the first day to Week 52 of the treatment period.

The estimate, its 95% CI (exact method), and p-value (Fisher's exact test) for between-group difference (MT-6548 – darbepoetin) should be calculated for the proportion of subjects receiving rescue therapy.

The analyses same to the above subjects receiving rescue therapy with ESA formulation should be performed for subjects receiving rescue therapy with RBC transfusion or receiving phlebotomy.

(3) Study drug dosage

1) Study drug dosage

Descriptive statistics of the mean daily dose of MT-6548 tablets and mean weekly dose of darbepoetin alfa injection (recombinant) should be calculated, after the first day of the treatment period, in each period between scheduled study visits and during the entire treatment period from the first day to Week 52 of the treatment period. The time course diagram for mean daily dose of MT-6548 tablets and mean weekly dose of darbepoetin alfa injection (recombinant) should be separately prepared by treatment group. 95% CI of the mean will be represented by an error bar. Each period between scheduled study visits is defined as the period between the scheduled study visit and the day before the next scheduled study visit.

2) Distribution of MT-6548 tablets and darbepoetin alfa injection

The number, proportion, and 95% CI (Clopper-Pearson [Exact] method) of the proportion per daily dose of MT-6548 tablets and per weekly dose of darbepoetin alfa (recombinant) during the treatment period should be provided by treatment group.

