### **8.6.10 Proportion of subjects with a documented Hb increase rate $>0.5$ g/dL/week**

The number and proportion of subjects with confirmed Hb increase rate of  $\geq 0.5$  g/dL/week, after the first day of the treatment period, in each period between scheduled study visits and during the entire treatment period from the first day to Week 24 of the treatment period should be provided for each treatment group. The Hb increase rate in this tabulation should be calculated based on the difference in Hb values in each period between scheduled study visits in every 4 weeks and the treatment interval obtained from the actual study visit date.

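### Hb-rise safety endpoint: the final SAP stops the whole-period proportion at Week 48 instead of Week 52, and both SAPs count rates of ≥0.5 g/dL/week where the protocol says >0.5

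*SAP*

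**What the plan says.** The protocol lists this safety endpoint as "Ratio of subjects with Hb increase rates exceeding 0.5 g/dL/week" (summary 7.2, with the same wording in 5.4.2 and 10.2). Its analysis section 13.3.3 says "Numbers and ratios of subjects with rate of Hb increase of >0.5 g/dL/week will be shown by treatment group". The protocol names no end week for the proportion.

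Final-data SAP 8.6.11 has a heading with >0.5 g/dL/week, but its text counts subjects at ≥0.5. It asks for the proportion in each period between scheduled visits and also "during the entire treatment period from the first day to Week 48 of the treatment period should be provided for each treatment group". The rate is based on "the difference in Hb values in each period between scheduled study visits in every 4 weeks", divided by the actual time between visits.

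The Definitions of Terms in the same SAP put completion of the treatment period at "Week 52 of the treatment period or the day of discontinuation during the treatment period".

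Phase 1 SAP 8.6.10 shows the same split between a heading with > and text with ≥. Its whole-period row, however, runs "during the entire treatment period from the first day to Week 24 of the treatment period should be provided for each treatment group", which is the last visit of that phase.

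**The concern.** Two rules in the operative text conflict with the rest of the plan. One shortens a period that the sentence itself calls entire. The other moves a boundary value from not counted to counted.

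The endpoint exists to detect excessive or acute Hb rises, and long-term safety is one of the trial's stated aims. A programmer who follows the text of 8.6.11 would produce a table whose title gives one threshold, whose content uses another, and whose overall row ignores rises in the last four weeks. A programmer who follows the heading would produce a different table. The published proportion would then not be the one the protocol defines.

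**Working it through.** The plan gives no figure for this endpoint, so there is nothing to reproduce. The check is a comparison of text, followed by an illustration of size.

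**Period.**
- Final SAP 8.6.9, the companion table for Hb ≥12.0 and ≥13.0 g/dL, runs "during the entire treatment period from the first day to Week 52 of the" treatment period.
- Final SAP 8.5.2 (rescue therapy, study drug dose, iron dose) runs "during the entire treatment period from the first day to Week 52 of the treatment period", and the liver-function table in 8.6.3 does the same.
- Protocol 9.2.3 schedules Hb at both Week 48 and Week 52, so the last interval can be computed.
- Week 48 is unlikely to label the start of the last interval, because the parallel Phase 1 sentence names its end visit (Week 24, not Week 20).
- The per-interval rows of 8.6.11 carry no Week 48 limit. Only the whole-period row is clearly cut short.

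**Threshold.**

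| Place | Rule |
|---|---|
| Protocol 7.2 (summary), 5.4.2, 10.2, 13.3.3 | >0.5 |
| Endpoint list, item (11) of section 3.2, both SAPs | >0.5 |
| Headings of 8.6.11 (final) and 8.6.10 (Phase 1) | >0.5 |
| Text of 8.6.11 (final) and 8.6.10 (Phase 1) | ≥0.5 |

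Section 10 of each SAP declares no change from the protocol. The errata deal with other sections.

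**Size of the Week 48 stop.** Non-overlapping four-week intervals end at Weeks 4, 8, …, 52, which makes 13, of which 12 end by Week 48. If overlapping spans are used while visits are two-weekly, there are 15, of which 14 end by Week 48. Section 8.6.11 does not say which applies. The row loses subjects whose only qualifying rise is in Weeks 48–52, so the loss cannot exceed the proportion with a rise in that interval. Assume a constant, independent chance p per interval and full retention (for overlapping spans, independence is only approximate):

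loss = p(1−p)^12 with 13 intervals, or p(1−p)^14 with 15 spans.

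| p (assumed) | Loss, 13 intervals | Loss, 15 spans | Subjects per 150 (13 / 15) | Upper bound, 150p |
|---|---|---|---|---|
| 0.5% | 0.47 points | 0.47 | 0.71 / 0.70 | 0.75 |
| 1% | 0.89 | 0.87 | 1.33 / 1.30 | 1.5 |
| 2% | 1.57 | 1.51 | 2.35 / 2.26 | 3.0 |
| 3% | 2.08 | 1.96 | 3.12 / 2.94 | 4.5 |

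**Size of the threshold change.** The rules differ only at exactly 0.5 g/dL/week, that is, when the rise in g/dL equals days/14. With Hb recorded to 0.1 g/dL (assumption), this can happen only at whole-week spacings: 1.5 over 21 days, 2.0 over 28, 2.5 over 35. Whole weeks are the usual spacing, because protocol 9.1 puts visits on the dialysis day after the two-day gap.

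For illustration, take 28-day spacing and a normal four-week change with mean 0. The planning SD of 1.73 with an assumed within-subject correlation ρ gives an SD of change of 1.73·√(2(1−ρ)), which is 0.77 at ρ = 0.9 and 1.09 at ρ = 0.8. Use 0.8 and 1.1, and add 0.6 as a lower assumption. Then

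- P(strictly above) = P(Z > 2.05/SD)
- P(tie) = P(Z > 1.95/SD) − P(Z > 2.05/SD)

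| SD | Strictly above | Tie | Tie ÷ above |
|---|---|---|---|
| 0.6 | 0.03% | 0.03% | 82% |
| 0.8 | 0.52% | 0.22% | 42% |
| 1.1 | 3.12% | 0.70% | 22% |

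**Both together.** The rule as intended gives 1 − (1 − above)^13. The rule as written gives 1 − (1 − above − w·tie)^12, where w is the share of intervals with whole-week spacing. As a simplification, the chance of a strict exceedance is taken as the same at other spacings.

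| SD | As intended | As written, w = 0 | w = 25% | w = 50% | w = 100% |
|---|---|---|---|---|---|
| 0.6 | 0.41% | 0.38% | 0.46% | 0.54% | 0.69% |
| 0.8 | 6.55% | 6.06% | 6.68% | 7.30% | 8.52% |
| 1.1 | 33.76% | 31.63% | 33.08% | 34.51% | 37.29% |

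The net change runs from −2.1 to +3.5 percentage points over the whole table, and from −0.03 to +0.28 points at SD 0.6.

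**The case against.** The strongest reply is that this is a small clean-up. The table is descriptive, both arms are treated alike, and high Hb values in Weeks 48–52 are still caught by the ≥12.0 and ≥13.0 g/dL table. The heading, endpoint list and protocol all agree on >0.5, so a careful programmer could work out the intended rule. The output-table list is not in the text available, so what was actually programmed is unknown. The protocol sets no end week, so the Week 48 point is a slip inside the SAP and not a departure from the protocol.

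The size estimates can also be challenged. The value 1.73 is an upper 95% confidence limit from another study, chosen for caution, and the correlation is assumed. Subjects enter with stable Hb and doses are adjusted to keep it in range, so a smaller SD is plausible. At SD 0.6 the net effect is under half a subject per 150.

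Most of this stands, and it limits the weight of the point. The percentages are illustrations, and the consequence is conditional on the text being followed. It does not remove the defect. The counting rule is stated in the operative text, that text contradicts its own heading, and no reason is given for either difference.

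**Conclusion.** Both points hold. The final SAP's whole-period row should end at Week 52 by the SAP's own definition and by its sibling tables. The threshold in the text of both SAPs contradicts their headings, their endpoint lists and the protocol.

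The documents alone establish that one interval is omitted (1 of 13, or 1 of 15 with overlapping spans) and that the two thresholds differ only at exactly 0.5 g/dL/week. Anything beyond that rests on the assumed event rates, SDs and visit spacing. On those, the effect ranges from negligible to a few percentage points, in either direction. Neither arm has an evident advantage, and the primary non-inferiority analysis, error rate and sample size are unaffected. The text should be corrected because it can change a reported protocol safety proportion, but the validity of the trial does not depend on it.

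**What to change.** 1. In final SAP 8.6.11, change the end of the whole-period proportion from Week 48 to Week 52.
2. In the text of final SAP 8.6.11 and Phase 1 SAP 8.6.10, change the threshold to greater than 0.5 g/dL/week.
3. Final SAP 8.5.4.3 records that the Phase 1 analysis has been run. If that table, or the final table after lock, is re-run, give the reason in the SAP and the study report and keep the result distinct from the original plan, as protocol 13.4 requires.

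The cost is one week number, one inequality in two places, and a re-run of one descriptive table (two if Phase 1 is also corrected). No new data are needed.
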